7.1.5. Statistical Analyses / Methods

The purpose of the primary analysis is to evaluate the association of biomarkers of the Renin Angiotensin System (RAS), specifically Ang II but secondarily Ang(1-7) with measures of RV function (specifically PASP and RV size ratio in the primary model, and also paradoxical septal motion on a more informal visual basis), whilst taking into account any observable variables that may confound the relationship between the two concepts.

RV function will be measured using PASP and RV size ratio. The general principle underlying all the analyses of RV function and RAS peptide biomarkers will be:

- model the joint distribution of PASP and RV size ratio as a function of the RAS peptide(s) in question (together with confounding variables also included as covariates),
- choose reference values of the RAS peptide(s) in question and estimate a posterior distribution of PASP and RV size ratio for those given values, and
- use the posterior distribution to determine the probability of RV dysfunction (for a future individual participant), defined (following the definition of moderate/severe pulmonary circulatory disease given in [Boissier, 2013](#)) as:
 - PASP > 40 mmHg
 - RV size ratio > 0.6

The advantage of this method is that all the information on the continuous scales of PASP and RV size ratio is maintained throughout the modelling process, and that dichotomising

participants into binary categories takes place at the end after the modelling has been done.

In order to evaluate the estimated effect of administering rhACE2 on RV outcomes (via its effect on the RAS peptides), predictions for the probability of RV dysfunction will be calculated for specific, pre-determined values of RAS peptide measurements that represent reasonable estimates for each RAS peptide both before and after dosing with rhACE2 in this patient population. These values will be hereafter referred to as *reference values* (the first reference value, hereafter referred to as the *pre-dose reference* and the second reference value, hereafter referred to as the *post-dose reference* reflect). Note: the terminology "pre-dose" and "post-dose" should not be taken to imply that investigational product is used in this study; these values should be taken as being borrowed from that interventional study. Furthermore, the term "reference values" in this context should not be interpreted as upper or lower limits to the normal range. They represent the best guess available for a patient's typical experience before and after rhACE2 administration.

Initially, the basic model described below would be attempted. If model convergence issues are encountered with that model it is unlikely that more complicated models involving covariates would fit, and covariate exploration may not be attempted. However, if covariate exploration is attempted the addition of covariates would be dependent on a combination of changes in DIC and expert judgement (including the biological rationale for the covariate and/or global structures of other statistical models fitted to comparable data types). To simplify reporting only model outputs from the final selected model would be formally reported (included in the CPSR), but a description / short justification for the selected model would be included in the CPSR.

At the time of writing, the reference values for Ang II (and for completeness Ang(1-7) and Ang(1-5)) were as follows:

	ANG II (pg/mL)	ANG 1-7 (pg/mL)	ANG 1-5 (pg/mL)
	Optional endpoint		
"Pre-dose" reference value	30.0	2.0	n/a
"Post-dose" reference value	8.0	30.0	n/a

An additional sensitivity analysis (to be computed alongside the above) in case the reference study values are discordant with the observed values will use the observed data to determine the references as follows

Sensitivity	ANG II (pg/mL)	ANG 1-7 (pg/mL)	ANG 1-5 (pg/mL) Optional endpoint
Sensitivity “Pre-dose” reference value	Upper Quartile of Observed ANG II	Lower Quartile of Observed ANG 1-7	Lower Quartile of Observed ANG 1-5
Sensitivity “Post-dose” reference value	Lower Limit of Quantification	Upper Quartile of Observed ANG 1-7	Upper Quartile of Observed ANG 1-5

The relationship between Ang II (as the explanatory variable) and the joint bivariate distribution of PASP and RV size ratio (the outcome variables) will be analysed using a Bayesian multivariate linear regression model.

The multivariate normal model is specified as follows:

$$\begin{pmatrix} y_{it1} \\ y_{it2} \end{pmatrix} \sim MVNormal \left(\begin{pmatrix} \mu_{it1} \\ \mu_{it2} \end{pmatrix}, \Sigma \right)$$

where y_{itj} represents the observed value for the i th participant, the t th time-point and the j th outcome (i.e. $j = 1$ representing PASP and $j = 2$ representing RV size ratio), μ_{itj} represents the expected value for the i th participant, t th time-point ($t = 1, 2, 3$) and the j th outcome ($j=1$ and $j=2$ as above), and Σ represents a variance-covariance (vcov) matrix for the two outcome variables.

The expected values, μ_{itj} , are modelled as follows:

$$\mu_{itj} = \alpha_j + \beta_j x_i + \gamma_{tj} z_{it}$$

where:

- α_j is the intercept term for the j th outcome (i.e. PASP or RV size),
- β_j represents the vector of slope coefficients for all participant-level variables in the model for the j th outcome,
- x_i represents the vector of observed participant-level variables values for the i th participant (if applicable – initial model structures would not involve such covariates but Age at Screening and Sex would be added first to be consistent with the study protocol),
- γ_{tj} represents the matrix of slope coefficients for all timepoint-level variables in the model for the j th outcome at time-point t ,
- z_{it} represents the matrix of observed time-point-level variables for the i th participant at time-point t (e.g. log10- transformed RAS).

The vcov matrix Σ is specified within each study participant, as a Kronecker product of the inter- and intra-marker vcov matrices Sigma and Tigma , respectively:

$$\Sigma = \text{Sigma} \otimes \text{Tigma}$$

(the notation \otimes represent the Kronecker product)

The $\mathbf{y}_{i=1,2}$ inter-marker vcov matrix

$$\text{Sigma} = \begin{pmatrix} \sigma_{y_1}^2 & \sigma_{y_1 y_2} \\ \sigma_{y_1 y_2} & \sigma_{y_2}^2 \end{pmatrix}$$

assumes a constant inter-marker bivariate correlation, $\rho_{y_1 y_2} = \sigma_{y_1 y_2} / \sqrt{\sigma_{y_1}^2 \sigma_{y_2}^2}$, across $\mathbf{y}_{t,i=1,2}$ measured at the same t . The Sigma vcov matrix structure, when $\sigma_{y_1 y_2} = 0$, implies independence between both markers.

The $\mathbf{y}_{i=1,2}$ inter-marker vcov matrix assumed as

$$\text{Tigma} = \begin{pmatrix} 1 & \rho & \rho^2 \\ \rho & 1 & \rho \\ \rho^2 & \rho & 1 \end{pmatrix}$$

implies an intra-marker AR(1) process structure with common correlation parameter ρ . The dimension of the T is determined by the number of timepoints ($t = 1, 2, 3$) the $\mathbf{y}_{i=1,2}$ marker measurements are measured at. Note: Initial simulation work showed an UN (Unstructured) form of vcov for Tigma results in convergence issues due to parameter estimation issues; hence why AR(1) is preferred. A potential drawback to using Kronecker product is that it forces the inter-marker relationship through time to be the same for both response variables; but the Kronecker product requires estimation of fewer parameters (improved chance of model convergence) and recognises the repeated measures (time) structure whilst allowing it to be handled as a nuisance parameter in the final inferences (albeit with the previous caveat).

Given the above assumptions the $\begin{pmatrix} \mathbf{y}_{i=1} \\ \mathbf{y}_{i=2} \end{pmatrix}$ vcov structure is derived as follows:

$$\Sigma = \text{Sigma} \otimes \text{Tigma} =$$

$$\begin{pmatrix} \sigma_{y_1}^2 & \sigma_{y_1 y_2} \\ \sigma_{y_1 y_2} & \sigma_{y_2}^2 \end{pmatrix} \otimes \begin{pmatrix} 1 & \rho & \rho^2 \\ \rho & 1 & \rho \\ \rho^2 & \rho & 1 \end{pmatrix} = \begin{pmatrix} \sigma_{y_1}^2 * \begin{pmatrix} 1 & \rho & \rho^2 \\ \rho & 1 & \rho \\ \rho^2 & \rho & 1 \end{pmatrix} & \sigma_{y_1 y_2}^2 * \begin{pmatrix} 1 & \rho & \rho^2 \\ \rho & 1 & \rho \\ \rho^2 & \rho & 1 \end{pmatrix} \\ \sigma_{y_1 y_2} * \begin{pmatrix} 1 & \rho & \rho^2 \\ \rho & 1 & \rho \\ \rho^2 & \rho & 1 \end{pmatrix} & \sigma_{y_2}^2 * \begin{pmatrix} 1 & \rho & \rho^2 \\ \rho & 1 & \rho \\ \rho^2 & \rho & 1 \end{pmatrix} \end{pmatrix}$$

Uninformative prior distributions are assigned for α , β , γ , Σ and Ω as follows:

- For each α_j outcome variable a normal distribution with mean zero, large variance (e.g. 1E6) would be used as a non-informative prior,
- each element in the vector β is assigned a distribution with the same specifications as for α ,
- each element in the matrix γ is assigned a distribution with the same specifications as for α and the elements of β ,
- S , defined as the inverse of Σ , is assigned an uninformative Wishart prior distribution: $S \sim \text{Wishart}(R, df)$ where: $R = \begin{pmatrix} 0.01 & 0 \\ 0 & 0.01 \end{pmatrix}$ and $df = 3$.
- The Ω parameter ρ is assigned uninformative uniform prior distribution over $[-1,1]$ interval.
- Note: Simulations suggest that the model convergence is improved if the response variables (or more specifically their covariance parameter estimates) are roughly on the same scale (range). Therefore, if required, the response variables may be re-scaled for model fitting, but model inferences/results should be displayed using the original scale of the response variable.
- Note: Simulation work suggests that model convergence may also be sensitive to the software used (due to the complexities of estimating the vcov parameters and the limitations of Gibbs samplers being most efficient when the priors are conjugate to the likelihood of the parameters; once a Kronecker Product vcov is involved the conjugacy is not spotted automatically by most software). The first intent is to use SAS PROC MCMC, but if that does not work then R may be used (e.g. an appropriate package that implements JAGS) and if R fails then Stan may be used. Although a Bayesian implementation of the above model is desired if convergence issues are encountered then SAS PROC MIXED may be used to estimate the required model parameters (it may also as part of the QC checking of the model)
- Note: For IA1 (and IA2 and final analysis, if required) model simplification may occur to improve model convergence (e.g. γ parameter would only contain terms for the RAS peptides and not other time dependent terms such as separate slopes for each visit and endpoint combination).
- The initial model structure would consist of nine parameters, a slope and intercept for the two linear regressions of RAS biomarker level against outcome (PASP or RV Size ratio) (four parameters), four parameters of Σ , and one parameter (ρ) for Ω

Estimates for the posterior distributions of coefficients in the model will be obtained using an MCMC simulation running a suitable number of chains for an appropriate number of iterations each to ensure satisfactory convergence of the MCMC sampling algorithm. Nominally, a minimum of 3 chains would be used to produce the Gelman-Rubin diagnostics, though these numbers may be adjusted as necessary and chain

convergence may require separate model runs (e.g. SAS PROC MCMC requires separate model runs to assess the Gelman-Rubin chain convergence (with a zero burn in); but the final MCMC model used for inference requires a non-zero burn in; necessitating separate modelling runs. However, the final model run should utilise one of the sets of starting parameters used in the Gelman-Rubin investigations).

The corresponding secondary pharmacodynamic analyses (using Ang(1-7), and optionally Ang(1-5), in place of Ang II) and a model including Ang II and Ang(1-7) as joint independent variables of interest may be used to support the primary analysis.

Details are provided in Section 7.2.

Posterior estimates for the predictive probability of RV dysfunction will be made for the two sets of reference values of Ang II described above (exception is if joint modelling using Ang II and Ang(1-7) is being attempted). If other covariates are included in the final inference model these predictions should be made using the observed mean value for continuous variables and the observed mode value for categorical variables (exception being terms like CENTRE or SEX which would be predict for the average of the corresponding levels). Note: Observed margins may be used if there is a good clinical rationale to do so (assessed on a covariate by covariate basis).

Details of the planned displays are provided in [Appendix 10: List of Data Displays](#) and will be based on GSK data standards and statistical principles.

Unless otherwise specified, endpoints / variables defined in Section 7.1.1 will be summarised using descriptive statistics, graphically presented (where appropriate) and listed.

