7. PHARMACODYNAMIC AND BIOMARKER ANALYSES

7.1. Primary Pharmacodynamic/Biomarker Analyses

7.1.1. Endpoint / Variables

The following variables may be included in the statistical model:

- Independent variable of interest:
 - Ang II on Study Days 1, 2 and 3 (after any imputations)
- Dependent (bivariate) variable of interest:
 - PASP on Study Days 1, 2 and 3
 - RV size ratio on Study Days 1, 2 and 3
- Potential covariates (to be explored, order listed indicates expected importance):
 - Centre
 - Age at screening
 - Sex
 - Use of vasopressors on Study Days 1, 2 and 3
 - PEEP on Study Days 1, 2 and 3
 - Proning status on Study Days 1, 2 and 3
 - BMI at screening
 - Concurrent use of inhaled nitric oxide on Study Days 1, 2 and 3
 - Mean airway pressure on Study Days 1, 2 and 3
 - Tidal Volume on Study Days 1, 2 and 3
 - ECMO on Study Days 1, 2 and 3
 - ECCO2R on Study Days 1, 2 and 3
 - SAPS II at screening
 - PaO₂/FiO₂ on Study Days 1, 2 and 3

Additionally, the presence/absence of paradoxical septal motion on Study Days 1, 2 and 3 may be assessed on an informal visual basis.

Note: Since the study was terminated early there may not be sufficient information in the collected data to explore covariate analyses and the covariate exploration process may not take place at all.

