7.1.5.1. Statistical Methodology Specification

Endpoint / Variables

 See above
Model Specification

 See above
Model Checking & Diagnostics

 “Bayesian Statistics Best Practice at GSK – Clinical Trials using Bayesian Inference” (effective 20-Apr-2017) gives guidance on model checking and diagnostics that would be applicable to the MCMC modelling in this study.
Model Results Presentation

 See above
Subgroup Analyses

 Not planned.
Sensitivity and Supportive Analyses

 See above. Only the final (chosen) model form would be used to produce the Tables/Listings/Figure outputs supporting the CPSR. If the joint modelling strategy fails then an alternative strategy would be to derive the RV

dysfunction status for each participant (using the same criteria) and analyse the collection of derived binary outcomes, accounting for the repeated measures made on each participant (e.g. logistic regression modelling techniques). The final logit model (including any covariates) would be used to determine the probabilities (and differences) for the sets of “pre and post” dose Ang II reference values to be fed into the decision-making criteria. Any such approach would be documented in the CSR.

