10.10.8. Statistical Modelling Tables

Statistical Modelling: Tables					
No.	Population	IDSL / Example Shell	Title	Programming Notes	Deliverable [Priority]
Preparatory Analysis					
5.1.	Evaluable	SM_T2 (BICORR_PHARM)	Bivariate Correlations of RAS Biomarkers with Pharmacodynamic Endpoints	
Consider three different measures of correlation:1) derived from the bivariate mixed effect model and its between-marker Sigma vcov matrix 2) Pearson correlation 3) Spearman correlation
 
A version of this output should be produced as soon as possible after the interim or final analysis has been triggered in order to enable the team to decide a) which covariates to include in the models and b) which of the conditional outputs (if any) to produce. List of continuous covariates to be provided at run time by statistician
	SAC 1

Statistical Modelling: Tables					
No.	Population	IDSL / Example Shell	Title	Programming Notes	Deliverable [Priority]
5.2.	Evaluable	SM_T2 (BICORR_CONT)	Bivariate Correlations of Ang II, Ang(1-7), PASP and RV Size Ratio with Continuous Covariates	
Consider three different measures of correlation:1) derived from the bivariate mixed effect model and its between-marker Sigma vcov matrix 2) Pearson correlation 3) Spearman correlation
 
A version of this output should be produced as soon as possible after the interim or final analysis has been triggered in order to enable the team to decide which covariates to include in the primary and secondary models.
 
List of continuous covariates to be provided at run time by statistician
	SAC 1
5.3.	Evaluable	SM_T3 (ECHO_RAS_CAT)	Summary Statistics of RAS biomarkers and Echocardiogram Endpoints by Categorical Covariates	
A version of this output should be produced as soon as possible after the interim or final analysis has been triggered in order to enable the team to decide which covariates to include in the primary and secondary models.
 
List of categorical covariates will be provided by statistician at time of analysis
	SAC 1

Statistical Modelling: Tables					
No.	Population	IDSL / Example Shell	Title	Programming Notes	Deliverable [Priority]
Statistical Modelling					

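### If covariates are explored, the primary model is chosen on the study data and reported alone; if they are not, the protocol's age and sex terms are lost without being declared

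*SAP*

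**What the plan says.** Protocol 10.3.1 gives the primary model as a Bayesian repeated-measures regression with log(Ang II), age and sex as fixed effects.

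SAP 7.1.5 starts elsewhere. Its initial structure has nine parameters: an intercept and an Ang II slope for each of the two outcomes, plus the covariance terms. Age and sex are not in it. They are described as the first to enter if participant-level covariates are used. SAP 7.1.1 lists 14 candidates under "Potential covariates (to be explored, order listed indicates expected importance", with age and sex among them. For entry, "the addition of covariates would be dependent on a combination of changes in DIC and expert judgement"; biological rationale and the structure of comparable models count towards that judgement. No DIC threshold is given.

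Tables 5.2 and 5.3 (SAP 10.10.8) are to be run once the analysis is triggered "in order to enable the team to decide which covariates to include in the primary and secondary models". The note to Table 5.1, which correlates RAS biomarkers with pharmacodynamic endpoints, gives the same purpose.

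On reporting, SAP 7.1.5 says that "only model outputs from the final selected model would be formally reported", though "a description / short justification for the selected model would be included in the CPSR". SAP 7.1.5.1 repeats the restriction: "Only the final (chosen) model form would be used to produce the Tables/Listings/Figure outputs supporting the CPSR".

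Because the study stopped early, SAP 7.1.1 adds that "the covariate exploration process may not take place at all". SAP 2.1 declares one change from the protocol analysis, the dropped Ang II/Ang(1-7) ratio model.

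**The concern.** SAP 7.1.5 says that the purpose of the primary analysis includes accounting for observable confounders of Ang II and RV function. DIC measures how well a model predicts PASP and RV size ratio. It does not measure how far a covariate shifts the Ang II slope, so a real confounder can be left out. The choice is also made after the team has seen the unadjusted association and the basic fit. The posterior from the chosen model treats that model as if it had been fixed in advance.

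The other branch has its own problem. Without exploration, the single reported model adjusts for nothing and is not the protocol's model.

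In either branch the reader gets one Ang II estimate for the primary objective, and cannot tell how much it depends on the model chosen.

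**Working it through.** **The plan's own figures.** Protocol 12.5.5 says that the planning simulations had no covariates, so the stated operating characteristics do not cover selection. Rebuilding them from the stated inputs (N = 50, SD of log Ang II 1.74, outcome correlation 0.5, reference values 55.4 and 7.1 pg/ml) gave success at 0.6/0.6 in 76.2% (stated 74.7%), futility at 0/0 in 99.4% (99.1%), and a mean difference of 34.0 points (33.9). Some intermediate cells differ more, such as futility at 0.3/0.3 (55.5% against 49.3%). None bears on this point.

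**How often noise gets in.** Under flat priors DIC is close to AIC. One continuous covariate adds two slopes (one per outcome), so it lowers DIC when the fall in deviance exceeds 2 × 2 = 4. For a pure-noise covariate in a large sample, the chance is P(χ² on 2 df > 4) = e^(−2) = 0.135. With 14 independent noise candidates, the chance that at least one qualifies at the first step is 1 − (1 − 0.135)^14 = 87%.

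**Bias of a model that omits confounders.** Suppose three independent confounders, each with correlation r with log Ang II and effect g (in SD) on the outcome. The omitted-variable bias in the Ang II slope is 3 × r × g:
- r = 0.3, g = 0.2: 3 × 0.3 × 0.2 = 0.18 SD
- r = 0.3, g = 0.3: 3 × 0.3 × 0.3 = 0.27 SD

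**Coverage.** The simulation used 1,500 datasets per setting, 14 candidates, forward selection on DIC (taken as AIC) for the bivariate outcome with Ang II always in, a true slope of 0.3 SD, and age and sex not among the confounders. Three visits follow AR(1) with ρ = 0.6, taken as known. The fixed set is age, sex, the three confounders and one other covariate. Entries are coverage of the nominal 95% interval for the Ang II slope on PASP, with bias in brackets.

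| Visits | N | g | Basic model | DIC-selected | Age and sex forced, then DIC | Fixed set |
|---|---|---|---|---|---|---|
| 1 | 25 | none | 95.0% | 86.5% | 87.1% | 94.8% |
| 1 | 25 | 0.2 | 87.2% (+0.18) | 83.7% (+0.07) | 84.1% | 94.8% |
| 1 | 25 | 0.3 | 78.8% (+0.27) | 82.3% (+0.08) | 84.0% | 94.8% |
| 1 | 50 | none | 95.3% | 92.3% | 92.3% | 94.9% |
| 1 | 50 | 0.2 | 77.5% (+0.18) | 85.5% (+0.07) | 86.5% | 94.9% |
| 1 | 50 | 0.3 | 59.7% (+0.27) | 84.3% (+0.06) | 85.4% | 94.9% |
| 3 | 25 | none | 95.2% | 94.1% | 94.1% | 95.7% |
| 3 | 25 | 0.2 | 69.1% (+0.18) | 86.3% (+0.06) | 86.5% | 95.7% |
| 3 | 25 | 0.3 | 45.7% (+0.27) | 88.9% (+0.04) | 88.6% | 95.7% |
| 3 | 50 | none | 95.1% | 93.9% | 94.1% | 94.5% |
| 3 | 50 | 0.2 | 43.8% (+0.18) | 88.5% (+0.03) | 88.6% | 94.5% |
| 3 | 50 | 0.3 | 15.3% (+0.27) | 92.8% (+0.01) | 93.0% | 94.5% |

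Monte Carlo error is about 1 point or less: √(0.85 × 0.15 / 1500) = 0.9 points. The bias of the basic model matches the formula. With one record, DIC dropped 53–63% of the true confounders at N = 25 and 36–57% at N = 50. At N = 100 with one record, coverage after selection was 93.5% without confounding and 87–91% with it. Runs with 12 candidates and stronger correlations (0.3–0.4 with log Ang II) took coverage down to about 76%.

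The predicted mean difference between two reference values is the slope times a constant, so its coverage is the same. The difference in probability of RV dysfunction was not simulated.

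**The case against.** *Exploration may never happen.* This stands. A reader might infer that the reported interval will be too narrow. The documents support only that it can be, and only if covariates are explored.

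*The rule is not mechanical.* Biological rationale, an ordered list, early entry of age and sex, and a written justification all count. This stands in part: strict forward DIC is a stand-in for judgement whose results cannot be simulated. But forcing age and sex in first raised coverage by at most about 3 points, and a justification supplies no alternative estimates. Early entry of age and sex might also be read as unconditional. However, SAP 7.1.1 counts them among the candidates whose exploration may be skipped.

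*The unadjusted picture is visible.* This stands in part. A reader might infer that nothing unadjusted will be shown, yet Table 5.1 and Figure 3.4 display the raw association and Table 5.2 much of the screening evidence. What is missing is the Ang II slope and the probability difference from any model but the chosen one.

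*The protocol model would do worse.* This is the strongest objection. A reader might infer that returning to age and sex restores 95% coverage. It does not. In separate runs with 12 candidates, no Ang II effect and three confounders other than age and sex, the age-and-sex model covered 71–78% at N = 30 and 57–63% at N = 50. DIC selection covered 77–84% and 82–86%. The 95% figure belongs to a fixed set that contains the confounders.

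*The stakes are low.* No formal hypothesis is tested (SAP 2.4) and the interim analyses were cancelled (SAP 3.1). This lowers the urgency. But Figure 5.1 still presents 95% credible intervals for the primary objective.

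**Conclusion.** The point holds in conditional form. If covariates are explored, the interval from the chosen model ignores the selection. With one record per participant and N = 25–50, its coverage is about 86–93% without confounding and about 76–86% with three assumed confounders. Much of the second shortfall is omitted-variable bias, not narrow width. With three visits the figures are about 94% and 86–93%, so the selection penalty alone nearly disappears. If exploration is skipped, there is no selection penalty. The reported model then omits every covariate, including the protocol's age and sex, and SAP 2.1 does not say so. Under the same assumed confounding its coverage ranges from 15% to 87% in the table.

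These sizes rest on assumptions that are not in the documents: the number of evaluable participants, confounder strength, a slope of 0.3 SD, visit correlation of 0.6, independent continuous covariates, and DIC applied without judgement. The reporting gap and the undeclared departure need none of them.

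**What to change.** In SAP 7.1.5, 7.1.5.1 and Table 5.4, always fit and report the protocol model (log Ang II, age, sex). Beside it, report the covariate-free model and any DIC-selected model, each with the Ang II slopes and the difference in probability of RV dysfunction. Declare any departure from the protocol model in SAP 2.1.

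If other confounders are to be adjusted for, name them from the existing ordered list before the RAS data are examined and keep them whatever the DIC. Age and sex alone do not remove confounding by other variables. The protocol model is there because it was fixed in advance, and the comparison shows how far the Ang II result depends on model choice.

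The cost is a few more pages of output. The basic model is fitted anyway, and Table 5.4 already allows extra pages for sensitivity reference values. The larger models may not converge with few participants; if one fails, the report should say so.
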